8. Documented history of a cerebral vascular event (stroke or transient ischemic attack), unstable angina, or myocardial infarction within 6 months prior to their first dose of study drug, or refractory congestive heart failure unresponsive to medical treatment.
9. Therapy with the following agents within the specified timeframe prior to first study treatment:
 - a. systemic anti-neoplastic or investigational agents within prior 14 days.
 - b. hematopoietic growth factors within 7 days (erythropoietin, granulocyte colony stimulating factor, granulocyte-macrophage colony stimulating factor, or thrombopoietin receptor agonists).
10. Known hypersensitivity to any excipient contained in the drug formulation of any study treatment.
11. Prior allogeneic hematopoietic stem cell transplant, for any indication.
12. Hypocellular MDS, defined as bone marrow cellularity <30% in subjects ≤60 years old or <20% cellularity in subjects >60 years old.
13. Candidates for allogeneic stem cell transplant at the time of screening.
14. History of clinically significant liver disease (e.g. liver cirrhosis) or ongoing alcohol abuse.

NUMBER OF SUBJECTS: Approximately 142 subjects; up to 36 in phase 1 and approximately 106 in phase 2

STUDY TREATMENT(S):

Test Product, Dose and Mode of Administration:

Phase 1 Portion:

Vadastuximab talirine (SGN-CD33A) every 4 weeks (after azacitidine on the last day of azacitidine administration) via IV push at 5 mcg/kg up to 20 mcg/kg (with possible de-escalation to 3 mcg/kg), based on the dose escalation.

Azacitidine 75 mg/m² SC or IV for 7 days (7 consecutive days or 5 days on/2 days off/2 days on), beginning on Day 1 of repeated 4-week cycles.

Phase 2 Portion:

Vadastuximab talirine or placebo every 4 weeks (after azacitidine on the last day of azacitidine administration) via IV push at the dose determined in the Phase 1 Portion.

Azacitidine 75 mg/m² SC or IV (at the Investigator's discretion) for 7 days (7 consecutive days or 5 days on/2 days off/2 days on), in repeated 4-week cycles.

Reference Therapy, Dose and Mode of Administration:

Inactive placebo matching vadastuximab talirine will be provided for the Phase 2 Portion.

DURATION OF TREATMENT: Study treatment consists of repeated 4-week cycles of combination treatment. Subjects may continue on study treatment until disease progression, relapse, or unacceptable toxicity, whichever comes first.

STUDY EVALUATIONS:

Efficacy Evaluations:

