9.1.1 Phase 1 Portion – Open-Label Dose Evaluation

Cohorts of 6 dose-limiting toxicity (DLT)-evaluable subjects will be enrolled in an open-label fashion to receive vadastuximab talirine in combination with azacitidine in 28-day cycles, starting at 5 mcg/kg vadastuximab talirine. The DLT-evaluable population will include all Phase 1 subjects who have completed at least Cycle 1 of treatment (Cycle 1 of treatment is completed when the patient receives the first dose of azacitidine on Day 1 of Cycle 2) *or* discontinued study treatment because of AEs, or for a safety-related reason before having had the opportunity to receive the first dose of azacitidine on Day 1 of Cycle 2. In the Phase 1 Portion of the study, DLTs will be defined as posttreatment grade 4 neutropenia or grade 4 thrombocytopenia lasting >42 days from the start of therapy, in the absence of evidence of active MDS, or any grade 3 or higher non-hematologic toxicity that is clearly NOT resulting from underlying MDS or azacitidine, with the exception of:

- a. Grade 3 allergic reaction, fatigue, asthenia, anorexia, or constipation
- b. Grade 3 nausea, vomiting, or diarrhea not requiring tube feeding or total parenteral nutrition or hospitalization
- c. Febrile neutropenia (which resolves with appropriate treatment or marrow recovery), infection, bleeding, or other expected direct complications of cytopenias due to active MDS

If 2 or more subjects in a 6-subject cohort have DLTs, that dose level will be considered to have exceeded the MTD. If 5 mcg/kg vadastuximab talirine in combination with azacitidine is considered tolerable (≤ 1 of 6 subjects experiences a DLT), a cohort of 6 DLT-evaluable subjects will receive 10 mcg/kg vadastuximab talirine and azacitidine. If 10 mcg/kg vadastuximab talirine in combination with azacitidine is considered tolerable, a cohort of 6 DLT-evaluable subjects will receive 15 mcg/kg, and if 15 mcg/kg vadastuximab talirine in combination with azacitidine is considered tolerable, a cohort of 6 DLT-evaluable subjects will receive 20 mcg/kg. If 5 mcg/kg vadastuximab talirine in combination with azacitidine is not considered tolerable (> 1 of 6 subjects experiences a DLT), a cohort of 6 DLT-evaluable subjects will receive 3 mcg/kg vadastuximab talirine and azacitidine. The dose-escalation plan is presented in [Figure 1](#).

Figure 1: Study Schematic – Phase 1 Portion

DLT = dose-limiting toxicity; MTD = maximum tolerated dose.

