Azacitidine will be given on 7 days per cycle, either on the first 7 days or 5 days on/2 days off/2 days on; vadastuximab talirine will be given after azacitidine on the last day of azacitidine administration in each cycle. Response assessments (bone marrow examination and complete blood count [CBC]) will be conducted on Day 22-29 of even-numbered cycles until CR, then every 4 cycles thereafter. Subjects may continue on study treatment until disease progression, relapse, or unacceptable toxicity. After discontinuation of study treatment, subjects who have not experienced progression or relapse will continue to be assessed for response every 4 months through 24 months after the end of treatment (EOT) or until initiation of another anticancer treatment, progression, or relapse, whichever comes first. All subjects will be contacted for survival status every 2 months after EOT in follow-up until death or study closure, whichever comes first. Safety will be monitored through the surveillance of AEs, laboratory test measures, physical examination findings, and concomitant medication records. An additional bone marrow examination will be conducted for research purposes for subjects in the Phase 1 Portion of the study only.

After 6 DLT-evaluable subjects have had the opportunity to complete at least Cycle 1 (Cycle 1 of treatment is completed when the patient receives the first dose of azacitidine on Day 1 of Cycle 2) of treatment in each planned dose cohort, the data will be aggregated and analyzed by an SMC (Section 13.6.9). Based on the evaluation of the data, including the incidence of DLT in each cohort, the SMC may recommend the dose of vadastuximab talirine for the Phase 2 Portion of the study at the time of the evaluation. If additional safety information is required to recommend a phase 2 dose, the SMC could recommend enrollment of up to 12 additional treated subjects to continue to evaluate the safety of the combination at vadastuximab talirine dose(s) of 3, 5, 10, or 20 mcg/kg. Subsequently, upon completion of dose escalation, up to 12 more expansion patients may be enrolled (maximum of 24 expansion patients total), at any dose level not previously shown to exceed the MTD, to further characterize safety, PK, and activity.

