## 1.0 Introduction

This statistical analysis plan (SAP) describes the statistical methods to be used during the reporting and analyses of data collected under Seattle Genetics, Inc. Protocol SGN33A-004, entitled “A phase 1/2 study of vadastuximab talirine (SGN-CD33A) in combination with azacitidine in patients with previously untreated International Prognostic Scoring System (IPSS) Intermediate-2 or High risk myelodysplastic syndrome (MDS)”. Results of the proposed analyses will become the basis of the final clinical study report (CSR) for this protocol.

This SAP should be read in conjunction with the study protocol and case report form (CRF). This version of the plan has been developed using the protocol dated 13 April, 2017 and CRF dated 29 August, 2017. Any further changes to the protocol or CRF may necessitate updates to the SAP.

The purpose of this plan is to provide specific guidelines from which the analysis will proceed. All planned analyses specified in this document will be performed. Any changes to this plan, in the form of “post hoc” or “data driven” analyses will be identified as such in the final clinical study report. Any changes will be reflected in amendments to this plan before the database lock, detailed below, or specifically documented in the clinical study report.

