### 3.2 Sample Size Considerations

Phase 1 Portion (minimum of 6 subjects per cohort): Six subjects are adequate to appropriately assess the safety profiles and DLT rates of differing dose levels of vadastuximab talirine in combination with azacitidine. If the true incidence rate of DLT is 10%, the probability of considering a dose level tolerable (ie,  $\leq 1$  of 6 subjects experiences a DLT) will be 88.6%. If the true incidence rate of DLT is 50%, the probability of considering a dose level tolerable will be 10.9%.

With this type of study design, the exact number of subjects needed to complete the Phase I Portion is unknown because it depends on the number of cohorts required to reach MTD. Approximately 24 subjects are expected to participate in the Phase 1 portion of this trial, assuming 4 dose-escalation cohorts of 6 subjects.

Phase 2 Portion (106 subjects): A sample size of 106 subjects will provide 85% power to detect a treatment difference in ORR, assuming an ORR of 30% for azacitidine alone vs 55% for the combination vadastuximab talirine with azacitidine, at a 2-sided 0.1 alpha level.

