### 7.1 Safety Monitoring Committee

During the Phase 1 Portion of the study, the SMC will monitor the trial for safety and dose limiting toxicities (DLTs). Each dose cohort will be evaluated for DLTs prior to enrolling the subsequent cohort. Sufficient trends in safety or toxicity identified by the SMC may result in

enrollment suspension or study termination, as recommended by the SMC. The SMC may also recommend predetermined or intermediate dose levels for dose escalation and/or expansion for the Phase 2 portion of the study based on review of safety and efficacy data. In the event of a death or emergence of a life-threatening acute or chronic toxicity within the safety reporting period, enrollment to the study will be temporarily halted until the SMC convenes to review the aggregate safety data to determine if enrollment will resume, and the appropriate dose level moving forward. Additionally, the investigators and the PRA Medical Monitor will meet regularly (via teleconference, see [section 7](#)) to assess safety on an ongoing basis.

Meetings will be held approximately 1 week after the last patient completes the DLT period. The DLT period is defined as the time from start of study therapy in Cycle 1 through the start of day 1 of Azacitidine during Cycle 2, or the time at which a patient discontinues treatment due to study treatment-related toxicity prior to receiving Day 1 Cycle 2 treatment. This will occur for each dose escalation cohort that has been initiated and on an ad hoc basis as needed based on emerging safety data.

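### The first Phase 1 safety block leaves out the planned 15 mcg/kg dose without a reason, and the synopsis ceiling of 36 Phase 1 subjects does not match the design text

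*Protocol*

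**What the plan says.** Protocol 9.1.1 starts escalation at 5 mcg/kg and moves through 10, 15 and 20, with 3 used only if 5 is not tolerated. The 15 mcg/kg level is explicit: if 10 is tolerable, "a cohort of 6 DLT-evaluable subjects will receive 15 mcg/kg".

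Two expansion provisions follow in the same section and in the synopsis. Under the first, if the SMC needs more safety information before recommending a Phase 2 dose, it may ask for up to 12 further subjects at "vadastuximab talirine dose(s) of 3, 5, 10, or 20 mcg/kg". The second reads "Subsequently, upon completion of dose escalation, up to 12 more expansion patients may be enrolled (maximum of 24 expansion patients total"), and these subjects may be treated "at any dose level not previously shown to exceed the MTD".

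The synopsis gives the enrolment figures as "Approximately 142 subjects; up to 36 in phase 1 and approximately 106 in phase 2".

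SAP 1.0 states: "This version of the plan has been developed using the protocol dated 13 April, 2017". SAP 3.1.1 repeats the first provision with the same four doses and stops there; the second is absent, and SAP 1.1 does not list this as a change from the protocol. SAP 3.2 says: "Approximately 24 subjects are expected to participate in the Phase 1 portion of this trial, assuming 4 dose-escalation cohorts of 6 subjects". It gives no maximum.

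**The concern.** There are two separate problems.

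The dose list excludes a level that the trial plans to test and could carry into Phase 2. Protocol 8.4.1 bases the recommended dose on the MTD. If 15 is tolerated and 20 is not, 15 is the natural candidate, and it is the one escalation level at which the SMC cannot use the first block. What is at stake is which block can supply further safety data at that dose, and how much.

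The enrolment ceiling in the synopsis cannot be obtained from the design text if escalation passes 10 mcg/kg and both blocks are used. Sites, review boards and the SMC need one answer on how many subjects Phase 1 may enrol, and the protocol gives two.

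**Working it through.** **Inputs.** Cohort size 6 DLT-evaluable subjects (protocol 9.1.1; 13.2 calls this a minimum). First block up to 12, second block up to 12, expansion maximum 24 (9.1.1). Phase 2 size 106 and stated ceilings 36 and 142 (synopsis).

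**The plan's own figures.** 36 + 106 = 142, so the synopsis total is internally consistent. After full escalation, 4 × 6 = 24, and 24 + 12 = 36. The ceiling of 36 is therefore reproduced for the full design only if one block of 12 is counted.

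**Phase 1 size by escalation path** (6 × number of cohorts + expansion, no replacements):

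| Levels opened (mcg/kg) | Cohorts | One block (+12) | Both blocks (+24) | Excess over 36 with both | Expansion places if 36 is binding |
|---|---|---|---|---|---|
| 5 and 3, or 5 and 10 | 12 | 24 | 36 | 0 | 24 |
| 5, 10, 15 | 18 | 30 | 42 | 6 | 18 |
| 5, 10, 15, 20 | 24 | 36 | 48 | 12 | 12 |

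Overall total after full escalation with both blocks: 48 + 106 = 154. This is 12 above 142, and 12/142 = 8.5%.

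**Why 48 is not a hard maximum.** Protocol 9.4.3.3 has enrolment continue until each cohort has enough evaluable subjects. Each non-evaluable subject who is replaced adds to the count.

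**The dose list, for 15 tolerated and 20 above the MTD.** Taking the listed doses in turn:
- 3 was not opened, because 5 was tolerable.
- 5 and 10 are below the candidate dose.
- 20 has just been shown to exceed the MTD.
- 15 is not listed.

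**Largest number of subjects possible at one dose**, with every available expansion place used there:
- at 10, or at a tolerated 20: 6 + 12 + 12 = 30;
- at 15: 6 + 0 + 12 = 18.

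So 15 can still be expanded, but only through the second block.

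**The case against.** A reader might infer that subjects would have to receive 20 mcg/kg before more data could be gathered at 15. SAP 7.1 gives some support: "Each dose cohort will be evaluated for DLTs prior to enrolling the subsequent cohort". On that basis the SMC could ask for extra subjects at 5 or 10 before moving up, but not at 15. The documents do not establish this. Protocol 9.1.1 ties the first block to recommending a Phase 2 dose, not to deciding on escalation, and can be read as placing it after all planned cohorts. The escalation rule itself has no extra-subject step at any dose. This is one possible reading and no more.

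A reader might also infer that 15 was deliberately closed to expansion. The second block opens it once escalation is complete. SAP 7.1 also says that the SMC may recommend predetermined or intermediate doses for escalation or expansion, which suggests no intent to exclude 15. An SAP sentence cannot amend the protocol's list, however, and SAP 3.1.1 repeats the four-dose list.

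On enrolment, the best defence is that 36 and 24 are separate ceilings and the lower one binds. Both expansion provisions are permissive, and two cohorts plus 24, or four cohorts plus 12, each give 36. That would be workable, but nothing in the protocol says that 36 limits expansion, whereas 9.1.1 states the 24 without qualification.

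The SAP's figure of 24 should not be read as a conflicting maximum. It is an expected count for the escalation cohorts, and SAP 3.2 says that the exact number is unknown. The missing second block is a documentation gap, since SAP 1.0 says that the SAP is to be read with the protocol.

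**Conclusion.** The point holds on both parts and is minor. One of the five named dose levels is missing from the first block without explanation. The consequence is that further safety data at 15 mcg/kg can come only from the second block of up to 12 subjects. The synopsis ceiling of 36 is exceeded by 6 after three cohorts and by 12 after four if both blocks are filled. Those figures assume exactly 6 subjects per cohort; replacements would raise them. With only two cohorts, or with one block after full escalation, 36 is not exceeded.

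The effect is confined to Phase 1 enrolment limits and dose options. Phase 1 is analysed descriptively (SAP 9.0), and the safety set includes every treated subject (SAP 6.2). Phase 2 power, alpha and sample size do not change.

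**What to change.** 1. In the synopsis, protocol 9.1.1 and SAP 3.1.1, change the first-block doses to 3, 5, 10, 15, or 20 mcg/kg, keeping the cap of 12.
2. Settle the Phase 1 number in one of two ways:
   - (a) keep 36 and 142, and state in the synopsis and 9.1.1 that expansion is limited so that Phase 1 does not exceed 36; or
   - (b) restate the synopsis as approximately 48 in Phase 1 and approximately 154 overall, excluding replacements for non-evaluable subjects.
3. Add the second block to SAP 3.1.1. In SAP 3.2, keep 24 as the expected escalation count and add the chosen Phase 1 limit.

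The wording changes are small, but protocol 16.2 requires any protocol change to be handled as an amendment. Option (b) also raises the stated enrolment by 12 and means updating the subject number in the consent form, because Appendix 18.2 lists the approximate number of subjects as a consent element. Option (a) adds no subjects, but after full escalation it leaves 12 expansion places instead of 24.

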9.1.2 Phase 2 Portion – Randomized, Placebo-Controlled

Subjects will be randomized in a 1:1 manner to one of the study arms described in Table 1. Randomization will be stratified by Eastern Cooperative Oncology Group (ECOG) performance status (0 vs 1 or 2) and IPSS score (Intermediate-2 vs High risk).

[figure not shown]
Table 1: Treatment Arms

Study Treatment		Treatment Arm	
		Experimental	Comparator
Open-Label Study Treatment	Azacitidine 75 mg/m ² SC or IV (at the Investigator's discretion) for 7 days	X	X
Blinded Study Treatment	Vadastuximab talirine (SGN-CD33A) every 4 weeks (after azacitidine on the last day of azacitidine administration) via IV push at SMC-recommended dose	X	
	Placebo every 4 weeks (after azacitidine on the last day of azacitidine administration) via IV push		X

IV = intravenous; SC = subcutaneous; SMC = Safety Monitoring Committee.

Subjects will receive vadastuximab talirine in combination with azacitidine in 28-day cycles, starting at the dose level of vadastuximab talirine determined in phase 1. Response assessments (bone marrow examination and CBC) will be conducted once between Day 22 and Day 29 of even-numbered cycles until CR, then every 4 cycles thereafter. Subjects may continue on study treatment until disease progression, relapse, or unacceptable toxicity. After discontinuation of study treatment, subjects who have not had progression or relapse will continue to be assessed for response every 4 months through 24 months after EOT or until initiation of another anticancer treatment, progression, or relapse, whichever comes first. All subjects will be contacted for survival status every 2 months after EOT in follow-up until death or study closure, whichever comes first. Safety will be monitored through the surveillance of AEs, laboratory test measures, physical examination findings, and concomitant medication records. An IDMC (Section 13.6.10) will also periodically assess the ongoing safety data and make recommendations to either continue evaluating the combination or to stop the study due to toxicity concerns. Figure 2 is a study schematic for the Phase 2 Portion.

Figure 2: Study Schematic – Phase 2 Portion

AZA = azacitidine; CR = complete response.

- a Subjects may continue to receive repeated cycles of treatment until disease progression, relapse, unacceptable toxicity, or other discontinuation criteria are met.
- b For subjects who discontinue without having experienced disease progression follow-up will include disease assessment (CBC and bone marrow) every 4 months for 24 months or until disease progression. Subjects will be followed every 2 months for survival until death or the end of the study.

Unblinding a subject's treatment assignment will be limited to emergency circumstances where knowledge of the treatment assignment would affect decisions regarding the management of the subject. In the event of such an emergency circumstance, a formal unblinding procedure will be followed to allow the Investigator to immediately access a

subject's treatment assignment. Information on study treatment assignment should not be distributed to any other personnel involved in the clinical trial.

9.1.3 Study Stopping Criteria

The SMC (Phase 1 Portion) or the IDMC (Phase 2 Portion) will provide recommendations to the Sponsor if either of the following criteria are met:

- [REDACTED]
- [REDACTED]

The Sponsor will pause enrollment and notify the FDA and other health authorities, as applicable, if the stopping criteria are met.

9.2 Discussion of Study Design

The Phase 1 Portion of this study is a dose-escalation design to balance subject safety and speed of accrual while minimizing the number of subjects exposed to subtherapeutic doses. [23] This is a standard design in clinical oncology development.

The Phase 2 Portion is a randomized, double-blind study. Randomization reduces the risk of bias in treatment allocation, and the double-blind methodology reduces the risk of bias in treatment or assessment.

The safety and efficacy assessments in both portions are standard and well accepted measures in clinical oncology.

9.3 Study Duration

Study treatment consists of repeated 4-week cycles of combination treatment. Subjects may continue to receive treatment until they experience disease progression, relapse, or unacceptable toxicity.

The estimated duration of study treatment through final primary analysis is approximately 51 months from enrollment of the first subject to completion of the last subject. All subjects will be contacted for survival status every 2 months after EOT in follow-up until death or study closure, whichever comes first.

9.4 Study Population

9.4.1 Inclusion Criteria

Subjects cannot be enrolled before all inclusion criteria (including test results) are confirmed.

Eligible subjects must meet the following criteria:

1. Subjects with cytologically/histologically confirmed MDS according to the WHO 2008 classification, that is determined to be Intermediate-2 (1.5-2-points) or High risk (≥ 2.5 points) according to the IPSS risk category, with $\geq 5\%$ and $< 20\%$ bone marrow blasts.
2. Previously untreated for MDS with the exception of transfusions, hematopoietic growth factors, or IST.
3. Age ≥ 18 years.
4. Eligible for therapy with azacitidine.
5. Life expectancy of at least 12 weeks.
6. ECOG performance status ≤ 2 .
7. The following baseline laboratory data:
 - a. white blood cell (WBC) count $< 20,000/\text{mcL}$; pre-study use of hydroxyurea to control WBC is acceptable up to 24 hours prior to first dose of study treatment.
 - b. direct bilirubin ≤ 2 x upper limit of normal (ULN) and/or total serum bilirubin ≤ 1.5 x ULN (or total serum bilirubin ≤ 3 x ULN for subjects with Gilbert's disease).
 - c. serum creatinine ≤ 2.5 x ULN and creatinine clearance ≥ 30 mL/min (calculated using the Cockcroft-Gault formula; [Section 11.7](#)).
 - d. alanine aminotransferase (ALT) and aspartate aminotransferase (AST) ≤ 3 x ULN.
8. Females of childbearing potential must have a negative serum or urine beta human chorionic gonadotropin (β -hCG) pregnancy test result within 7 days prior to the first dose of study treatment. Females of non-childbearing potential are those who are postmenopausal greater than 1 year or who have had a bilateral tubal ligation or hysterectomy.
9. Females of childbearing potential and males who have partners of childbearing potential must agree to use 2 effective contraception methods during the study and for 6 months following the last dose of study drug.

Acceptable methods of contraception include: hormonal (birth control pills, injections, implants), intrauterine device (IUD), intrauterine hormone-releasing system (IUS), vasectomy (for males), barrier methods (male and female condoms, diaphragms, and spermicides), and complete abstinence. Complete abstinence is acceptable when this is in line with the preferred and usual lifestyle of the patient. (Periodic abstinence [eg, calendar, ovulation, symptothermal, post-ovulation methods] and withdrawal are not acceptable methods of contraception.)

10. Subjects must provide written informed consent.

